4.6 Exploratory efficacy analyses

Exploratory endpoints will not be statistically tested. As with the primary and secondary efficacy analyses, separate models will be used for dapagliflozin and saxagliptin analyses, and each analysis will include the (common) placebo group. Exploratory analyses will be performed for overall dapagliflozin and overall saxagliptin separately, by combining all treatment groups (low-dose and high-dose).

Details are provided below.

4.6.1 Exploratory efficacy endpoints for short-term period

These analyses will be conducted on the Randomised Subjects Data Set and the comparisons will be between overall dapagliflozin (or saxagliptin) and placebo.

4.6.1.1 Analysis of subjects requiring glycaemic rescue medication or discontinuing study medication due to lack of efficacy

The proportion of subjects requiring glycaemic rescue medication or discontinuing study medication due to lack of efficacy at or prior to Week 26 will be analysed between overall drug treatment (low-dose and high-dose) and placebo using a logistic regression.

This will be analysed using a logistic regression and summarised as described in Section 4.1.10. No weights will be used in the logistic regression for this analysis.

In addition, this analysis will be repeated for the subgroup of subjects on a stable baseline dose of metformin IR or XR (with or without insulin).

4.6.1.2 Time to glycaemic rescue medication or discontinuation of study medication due to lack of efficacy

A time-to-event analysis (where event is first use of rescue medication or discontinuation of study medication due to lack of efficacy, whichever is earlier) during the 26-week treatment period will be analysed using a Cox proportional hazards model as described in Section 4.1.11. Estimates of the hazard ratio and 95% CI will be provided.

In addition, an analysis based on Kaplan-Meier estimates will be calculated and 95% CIs and nominal p-value from a pairwise log rank test will be presented.

Rules for censoring are described in Section 4.1.11.

In addition, both analyses will be repeated for the subgroup of subjects on a stable baseline dose of metformin IR or XR (with or without insulin). No Kaplan-Meier plot will be presented for the subgroup analysis.

4.6.1.3 Percentage of subjects who initiate glycaemic rescue medication

The number and percentage of subjects who require glycaemic rescue medication during the 26-week treatment period will be provided.

In addition, this analysis will be repeated for the subgroup of subjects on a stable baseline dose of metformin IR or XR (with or without insulin).

4.6.2 Exploratory efficacy endpoints for short-term and long-term period

These analyses will be conducted on the Randomised Subjects Data Set and the comparisons will be between overall dapagliflozin (or saxagliptin) and placebo.

These analyses will first be presented without considering the third randomisation, i.e. including all subject's data up to Week 52 or last visit (if earlier than Week 52). Then, to account for the randomised withdrawal of background metformin at Week 32 or Week 40, additional analyses will be performed:

- Additional weighted analyses of change in HbA1c, FPG, and the percentage of subjects with HbA1c < 7% will be performed excluding subjects randomised to withdraw from

metformin (Sections 4.6.2.1 and 4.6.2.2). For the weighted analyses, dapagliflozin (or saxagliptin) subjects who went through the third randomisation and withdrew metformin will be assigned a weight of 0, and those randomised to stay on metformin will be assigned a weight of 2. All other dapagliflozin (or saxagliptin) subjects will be assigned a weight of 1. Placebo subjects randomised to withdraw metformin and switch to active treatment will be assigned a weight of 0. Placebo subjects randomised to stay on metformin will be assigned a weight of 3. All other placebo subjects will be assigned a weight of 1. For this analysis, subjects with a weight of 0 will be excluded from the summary statistics, multiple imputation steps, and ANCOVA/logistic regression model.

4.6.2.1 Analysis of change from baseline at Week 52 in HbA1c and FPG

Change from baseline at Week 52 in HbA1c and, separately, FPG will be analysed using the ANCOVA model described in Section 4.1.9. This analysis includes all data regardless of rescue medication initiation or adherence. The analysis will be evaluated in each imputed data set and the results will be combined using Rubin's rules as described in Section 4.1.12.4. Missing data in values of HbA1c at Week 52 will be imputed using the multiple imputation approach described in Section 4.1.12. Point estimates and 2-sided 95% CIs for the mean change within each treatment group, as well as the difference in mean change between each drug and placebo will be calculated. Nominal p-values will be presented. No weights will be used in the multiple imputation or ANCOVA for this analysis.

Additional analyses for change from baseline in HbA1c and FPG will be performed at Week 6, Week 12, Week 20, Week 26, Week 32 and Week 40. Data will be multiply imputed based on the same approach as described for the in Section 4.5.4, and will include all data regardless of rescue medication initiation or adherence. Analyses will be based on the same multiply imputed data sets produced for Week 52 assessments. Analysis will be performed by fitting the same ANCOVA model as the one described above and in Section 4.1.9. The analysis model will be evaluated in each imputed data set and the results will be combined using Rubin's rules as described in Section 4.1.12.4 for each visit.

In addition, a line plot of LS means \pm 95% confidence interval (CI) by visit up to Week 52 will be displayed for both HbA1c and FPG.

4.6.2.2 Analysis of the percentage of subjects with baseline HbA1c \geq 7% who achieve a HbA1c level $<$ 7% at Week 52

Data will be multiply imputed based using the same approach as described for the primary analysis in Section 4.4.1, and will include all data regardless of rescue medication initiation or adherence. HbA1c response ($<$ 7%) will be derived from dichotomising the imputed continuous values of HbA1c and Rubin's rules will be used to combine analyses across the multiple imputations. The proportion of responders (subjects achieving an HbA1c $<$ 7% at Week 52) will be analysed using logistic regression and summarised as described in Section 4.1.10. No weights will be used in the multiple imputation or logistic regression for this analysis.

4.6.2.3 Analysis of subjects requiring glycaemic rescue medication or discontinuing study medication due to lack of efficacy

The proportion of subjects requiring glycaemic rescue medication or discontinuing study medication due to lack of efficacy at or prior to Week 52 will be analysed between overall drug treatment (low-dose and high-dose) and placebo using a logistic regression.

This will be analysed using a logistic regression and summarised as described in Section 4.1.10. No weights will be used in the logistic regression for this analysis.

4.6.2.4 Time to glycaemic rescue medication or discontinuation of study medication due to lack of efficacy

A time-to-event analysis (where event is first use of rescue medication or discontinuation of study medication due to lack of efficacy, whichever is earlier) during the 52-week treatment period will be analysed using a Cox proportional hazards model as described in Section 4.1.11. Estimates of the hazard ratio and 95% CI will be provided.

In addition, an analysis based on Kaplan-Meier estimates will be calculated and 95% CIs and nominal p-value from a pairwise log rank test will be presented.

Rules for censoring are described in Section 4.1.11.

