Time to initiation of glycemic rescue medication or discontinuation of study medication due to lack of efficacy during the 52-week treatment period will be analyzed using a Cox proportional hazards model with stratification factors as covariates. Estimates of the hazard ratio and 95% confidence intervals will be provided. Kaplan-Meier estimates will be calculated and plotted by treatment group. For the analysis during the 52-week treatment period, all subjects will be censored at the Week 52 visit date or last study date (for those withdrawing from the study prior to Week 52 visit), if rescue or treatment discontinuation due to lack of efficacy has not occurred by then. These analyses will use subjects from the Randomized Subjects Data Set.

To account for the randomized withdrawal of background metformin at Week 32 or Week 40, additional weighted analyses of change in HbA1c, FPG, and the percentage of subjects with HbA1c < 7% will be performed excluding subjects randomized to withdraw from metformin. For the weighted analyses, dapagliflozin (or saxagliptin) subjects who went through the third

randomization and withdrew metformin will get a weight of zero, and those randomized to stay on metformin will get a weight of 2. All other dapagliflozin (or saxagliptin) subjects will get a weight of 1. Placebo subjects randomized to withdraw metformin and switch to active treatment will get a weight of zero. Placebo subjects randomized to stay on metformin will get a weight of 3. All other placebo subjects will get a weight of 1. ANCOVA models will be utilized for the weighted analyses of change in HbA1c and FPG, and a logistic regression model will be used for the weighted analysis of the percentage of subjects with HbA1c < 7%.

Exploratory efficacy analysis for monotherapy assessment

These analyses will be conducted during the randomized withdrawal period using the Randomized Withdrawal Subjects Data Set.

The reference time point to be used as 'withdrawal baseline' will be the closest time point on or before the third randomization visit. The following endpoints will be assessed:

- Change from withdrawal baseline in HbA1c
- Change from withdrawal baseline in FPG
- Percentage of subjects who achieve or maintain a HbA1c level < 7.0% at the end of the withdrawal period
- Time to rescue therapy initiation or discontinuation of study medication due to lack of glycemic control during the withdrawal period using withdrawal baseline as the reference time point

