- Eligible subjects who are receiving active treatment will be grouped into two separate strata for dapagliflozin and saxagliptin, and then randomised 1:1 within each strata to either discontinue background medication with metformin or to continue background medication with metformin. For subjects on active treatment who are randomised to withdraw background medication with metformin, those who are currently receiving high doses of saxagliptin (5 mg) or dapagliflozin (10 mg) will continue to receive the high doses, whereas subjects who are currently receiving low doses of saxagliptin (2.5 mg) or dapagliflozin (5 mg) will have their doses up-titrated to the high doses (saxagliptin 5 mg or dapagliflozin 10 mg). Subjects in the active treatment arms who are randomised to continue background medication with metformin will continue with their current dose of either saxagliptin or dapagliflozin.
- Eligible subjects who are receiving placebo will be randomised 1:1:1 to either withdraw background medication with metformin and switch to active treatment with either saxagliptin 5 mg or dapagliflozin 10 mg or to remain on background medication with metformin and continue with placebo.

[figure not shown]
The study design schematic for subjects not undergoing randomised withdrawal of background medication at Week 32 or Week 40 is presented in [Figure 2](#).

Figure 2 Study design schematic for subjects not undergoing randomised withdrawal of background medication at Week 32 or Week 40

The study design schematic for subjects undergoing randomised withdrawal of background medication at Week 32 or Week 40 is presented in [Figure 3](#).

[figure not shown]
Figure 3 Study design schematic for subjects undergoing randomised withdrawal of background medication at Week 32 or Week 40

*Subjects who fail to qualify at Week 26 due to HbA1c ≥ 7.5% at Week 26 may qualify at Week 32 if HbA1c < 7.5% at Week 32.

The subgroups following the third randomisation at Week 32 or Week 40 are presented in [Figure 4](#).

Figure 4 Subgroups following the third randomisation at Week 32 or Week 40

^a Subjects who fail to qualify for the third randomisation due to HbA1c ≥ 7.5% at Week 26 may qualify at Week 32 if HbA1c < 7.5% at Week 32.

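### The 52-week rescue analyses lack the weighted version that SAP 4.6.2 gives the other Week 52 endpoints, so after Week 32 they mildly dilute the drug-placebo comparison on background therapy

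*SAP*

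**What the plan says.** **Third randomisation.** SAP 1.2 states that eligible placebo subjects "will be randomised 1:1:1 to either withdraw background medication with metformin and switch to active treatment", or stay on placebo plus metformin. Eligible subjects on either drug are randomised 1:1 to stop or keep metformin. Only subjects on metformin alone with HbA1c below 7.5%, not rescued and still on study drug, can enter.

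**Correction for some endpoints.** SAP 4.6.2 opens with "These analyses will first be presented without considering the third randomisation, i.e. including all subject's data up to Week 52". To allow for the randomised withdrawal it then adds: "Additional weighted analyses of change in HbA1c, FPG, and the percentage of subjects with HbA1c < 7% will be performed". Subjects randomised to stop metformin get weight 0 and are left out, drug continuers get 2, placebo continuers 3 and everyone else 1. Protocol 8.4.2.3 limits the correction to the same three endpoints.

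**Rescue endpoints.** For the 52-week proportion, SAP 4.6.2.3 says "No weights will be used in the logistic regression for this analysis". For time to event, SAP 4.6.2.4 says it "during the 52-week treatment period will be analysed using a Cox proportional hazards model as described in Section 4.1.11", with Kaplan-Meier estimates and a nominal log-rank p-value. The protocol's rule is that "all subjects will be censored at the Week 52 visit date or last study date"; SAP 4.1.11 is similar, and neither mentions the switch or metformin withdrawal. In SAP Table 23 the column that excludes subjects randomised to withdrawal is empty for every rescue row.

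**The concern.** After the third randomisation, a rescue in a placebo child now taking dapagliflozin or saxagliptin alone counts as a placebo event. A rescue in a drug child who has stopped metformin counts as an event for drug with its background therapy. The plan treats this as worth correcting for three Week 52 endpoints, and uses the same weights for safety (W3 in SAP 4.7), but not for rescue. SAP Table 12, which lists changes from the protocol, gives no reason.

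Rescue is also somewhat exposed to the switch. Metformin is withdrawn openly, the investigator may be partly unblinded (SAP 1.4), and starting insulin after the Rescue Visit is at the investigator's discretion (Protocol 3.7.2). At stake is how the 52-week hazard ratio, cumulative percentages and odds ratio are read. The primary and secondary inference is not affected.

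**Working it through.** **Plan's own figures.** The weights are inverse randomisation probabilities: 1/(1/2) = 2 for drug continuers and 1/(1/3) = 3 for placebo continuers. Everyone re-randomised is unrescued and on drug at that point, so each weighted continuer group stands for its whole eligible group. The same fixed weights therefore suit the rescue endpoints. The documents state no rescue rate, eligible share or power for these endpoints.

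**Head counts (assumed shares, 81 per arm from SAP 1.2).** Assume 40–60% on metformin only, 25–45% of these eligible, and 30–45% of the arm already rescued or out by Week 32.
- Re-randomised per arm: 81 × 0.40 × 0.25 = 8.1 to 81 × 0.60 × 0.45 = 21.9.
- Placebo switchers (2/3): 5.4 to 14.6. Share of the late placebo risk set: 5.4/(81 × 0.70) = 10% to 14.6/(81 × 0.55) = 33%.
- Drug subjects withdrawn from metformin (1/2): 4.1 to 10.9. Share of the late risk set: 7% to 25%.

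**Full 52-week hazard ratio.** Assume weekly placebo hazards of 0.008 (eligible) and 0.02 (others), a hazard ratio of 0.6 in each group, monotherapy at 1 to 3 times the eligible placebo hazard, follow-up from Week 6 and all switches at Week 32. Large-sample Cox fits, with 8 to 22 eligible per arm, give:

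| Version | Hazard ratio |
|---|---|
| As planned | 0.608–0.622 |
| Weights 0/2/3/1 | 0.604–0.610 |

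The shift is about 0.004 to 0.012. A rerun that instead counts the 8 to 22 as event-free at Week 32 gives overall limits of about 0.002 to 0.014. Values sit slightly above 0.60 because two hazard groups are pooled.

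**Harsher assumption.** Suppose re-randomised subjects have the same rescue hazard as everyone else (placebo 0.012 per week, true hazard ratio 0.50) and 20–60% of those event-free at Week 32 are re-randomised. The planned hazard ratio is then 0.51–0.56. The weighted fit returns 0.50 wherever it ran; two of three fits at 60% failed numerically. Equal hazards are hard to square with an entry rule of HbA1c below 7.5%.

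**52-week proportion.** Assume rescue by Week 32 of 0.30 (placebo) and 0.20 (drug); later risk of 0.30 and 0.25 in subjects not re-randomised, and of 0.20 and 0.10 in eligible subjects who continue; monotherapy risk 0.20; and 20% of each arm re-randomised.
- On background therapy: placebo 0.30 + 0.50 × 0.30 + 0.20 × 0.20 = 0.49; drug 0.20 + 0.60 × 0.25 + 0.20 × 0.10 = 0.37. Odds ratio (0.37/0.63)/(0.49/0.51) = 0.61.
- As planned: placebo late risk 0.20/3 + (2/3) × 0.20 = 0.20, so 0.49 again; drug late risk 0.5 × 0.10 + 0.5 × 0.20 = 0.15, so 0.38. Odds ratio (0.38/0.62)/(0.49/0.51) = 0.64.

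With 10–40% re-randomised and monotherapy risk 0.10–0.40, odds ratios of 0.58–0.63 become 0.61–0.65.

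**Precision.** The two-group model yields about 72 to 81 events for one drug against placebo. The standard error of the log hazard ratio is about 2/√events. Around 0.615, the 95% interval is 0.39–0.98 with 72 events and 0.40–0.95 with 81, far wider than the shift.

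**The case against.** The strongest reply is that the plan is consistent with its objectives. The 52-week HbA1c, FPG and responder objectives speak of add-on treatment or therapy, and exactly those three have a weighted version. The time-to-rescue objective does not use the term; its metformin and insulin clause describes the population. The proportion-rescued objective covers 26 weeks only. This stands: the documents do not show that the plan contradicts a stated add-on objective for rescue, although a reader might infer it.

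A reader might also infer that the 52-week hazard ratio no longer compares drug with placebo at all. That is not supported. All follow-up before Week 32, and all later follow-up in insulin users, in subjects with HbA1c of 7.5% or more and in continuers, remains drug versus placebo on background therapy. The SAP also says openly that these analyses ignore the third randomisation.

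Three further points stand. SAP 4.6 says exploratory endpoints will not be statistically tested. The eligible counts may be smaller than assumed: subjects recruited before the third amendment took effect at their site could decline, some passed Week 32 or 40 too early, and long visit delays barred entry. The 26-week rescue analyses are unaffected.

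None of this fills the gap. The Kaplan-Meier and rescue summaries for the withdrawal period (SAP 4.6.3.3 and 4.6.3.4) compare subjects within original arms, and are not a corrected 52-week comparison of drug with placebo.

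**Conclusion.** The omission is real: the 52-week logistic, Cox, Kaplan-Meier and log-rank analyses of rescue have no version that accounts for the third randomisation, while the other Week 52 efficacy endpoints do. The planned analysis is valid for the originally assigned arms. Read as drug versus placebo on background therapy, it is mildly diluted after Week 32.

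The effect is small. On the two-group assumptions the hazard ratio moves by roughly 0.00 to 0.01 towards 1; on the harsher equal-hazard assumption, by up to about 0.06. These sizes rest wholly on assumed hazards and eligible shares. The endpoints are exploratory, so this is a cheap improvement in consistency and does not threaten the trial's conclusions.

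**What to change.** Keep the planned analyses. Add a supportive weighted version to SAP 4.6.2.3 (logistic regression) and 4.6.2.4 (Cox, Kaplan-Meier and log-rank), and fill the empty Table 23 cells. Use the plan's own subject-level weights: 0, and so excluded, for subjects randomised to withdraw metformin; 2 for drug continuers; 3 for placebo continuers; 1 for all others. Use a robust variance. Base any 52-week statement about rescue on background therapy on this version. Censoring at the third randomisation with date-dependent weights would be a different method from the plan's and does not carry over directly to the logistic regression.

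No new data are needed, only SAP wording and a little programming. The price is precision, because only about 3 to 7 placebo continuers would carry weight 3. Using (sum of weights)²/(sum of squared weights), the effective late placebo risk set falls from 57 to 56.7²/(48.6 + 9 × 2.7) = 44 at the low end of the assumed range, and from 45 to 44.55²/(22.68 + 9 × 7.29) = 22 at the high end.

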4.6.2.5 Percentage of subjects who initiate glycaemic rescue medication

The number and percentage of subjects who require glycaemic rescue medication during the 52-week treatment period will be provided.

In addition, this analysis will be repeated for the subgroup of subjects on a stable baseline dose of metformin IR or XR (with or without insulin).

4.6.3 Exploratory efficacy analyses for monotherapy assessment during the randomised withdrawal period

These analyses will be conducted during the randomised withdrawal period using the Randomised Withdrawal Subjects Data Set.

The endpoints will be summarised within each treatment group (as defined in Section 2.1) from the original randomisation as follows:

- For subjects initially randomised the dapagliflozin (or saxagliptin) group, the subjects re-randomised to withdraw metformin will be compared to the subjects re-randomised to stay on metformin. Separate analyses will be performed for subjects respectively randomised to either dapagliflozin or saxagliptin group.
- For subjects initially randomised to the placebo group, the subjects who were re-randomised to switch to dapagliflozin (or saxagliptin) monotherapy will be compared to the subjects who were re-randomised to stay on placebo with background metformin. Separate analyses will be performed respectively for subjects re-randomised to

dapagliflozin and for those re-randomised to saxagliptin, using the those re-randomised to placebo as comparator.

4.6.3.1 Observed and change from withdrawal baseline in HbA1c and FPG

Descriptive summaries of observed and change from withdrawal baseline in HbA1c and, separately, FPG for withdrawal baseline and post-withdrawal baseline visits will be provided. This analysis will include all data regardless of rescue medication initiation or adherence. No imputation will be performed.

4.6.3.2 Percentage of subjects who achieve or maintain a HbA1c level < 7% at the end of the withdrawal period

The number and percentage of subjects who achieve or maintain a HbA1c level < 7% at the end of the withdrawal period will be provided. This analysis will include all data regardless of rescue medication initiation or adherence. No imputation will be performed.

4.6.3.3 Time to glycaemic rescue medication or discontinuation of study medication due to lack of efficacy

A time-to-event analysis (where event is first use of rescue medication or discontinuation of study medication due to lack of efficacy, whichever is earlier) during the 52-week treatment period will be analysed. Date of first dose will be date of first dose in the randomised withdrawal period. Kaplan-Meier estimates will be calculated, and 95% CIs will be presented. No Kaplan-Meier plot will be presented for this analysis.

Rules for censoring are described in Section 4.1.11.

